3.2 Selection of Study Population

3.2.1 Inclusion Criteria

Patients may be entered in the study only if they meet all of the following criteria:

1. Male or female patients aged at least 18 years.
2. Histologically-confirmed, without B symptoms, Ann Arbor stage II to IVA NHL (CD20+ FL of Grades 1, 2, or 3a) (Appendix 5):
 - Patients can be entered based on a diagnosis of CD20+ follicular lymphoma confirmed at the investigational site. Archival tissue or slides must be sent to the central pathology reviewer for retrospective confirmation of diagnosis. Patients must have tissue or slide available for the central pathology review to be enrolled.
 - Patients having both diffuse and follicular architectural elements will be considered eligible if the histology is predominantly follicular (i.e., $\geq 50\%$ of the cross-sectional area), and there is no evidence of transformation to a large cell histology.
 - If the interval since tissue diagnosis of follicular lymphoma is >24 months prior to screening visit, diagnostic confirmation using either core needle or excisional lymph node biopsy (latter preferred) is required to confirm that the histology remains in one of the eligible categories.
 - Bone marrow biopsy alone is not acceptable.
3. Low tumor burden according to GELF criteria defined as:
 - a) Normal serum lactate dehydrogenase (LDH)
 - b) No mass ≥ 7 cm.
 - c) Less than 3 nodal sites, each with diameter >3 cm.
 - d) No systemic or B symptoms (fever $>38^{\circ}\text{C}$ for 3 consecutive days; recurrent, drenching night sweats; unintentional weight loss exceeding 10% body weight in the last 6 months.
 - e) No splenomegaly ≥ 16 cm by CT scan.
 - f) No risk of vital organ compression.
 - g) No pleural or peritoneal serous effusion.
 - h) No cytopenias (defined as platelets $<100 \times 10^9/\text{L}$ ($100,000/\text{mm}^3$), hemoglobin <100 g/L (10 g/dL), or absolute neutrophil count $<1.5 \times 10^9/\text{L}$ ($1,500/\text{mm}^3$)).

4. Patients not previously treated for their FL, including any previous treatment for FL under clinical trials except localized radiation therapy for previous limited stage disease.
5. Eastern Cooperative Oncology Group (ECOG) performance status of 0 to 1 (Appendix 6).
6. Have at least one measurable lesion of at least 1.5 cm in longest diameter as per the IWG criteria 2007 (Appendix 4) at screening (lesion clearly measurable in at least 2 perpendicular dimensions).
7. Adequate renal function: Creatinine clearance ≥ 0.835 mL/s (50 mL/min) (Cockcroft-Gault formula)
8. Adequate liver function: total bilirubin <34 $\mu\text{mol/L}$ (2.0 mg/dL) except for patients with Gilbert's Syndrome or hemolysis. Aspartate aminotransferase (AST) and alanine aminotransferase (ALT) $<3 \times$ upper limit of normal (ULN) ($<5 \times$ ULN is acceptable if abnormalities are thought to be related to hepatic infiltration by FL).
 - Patients with total bilirubin ≥ 34 $\mu\text{mol/L}$ (2.0 mg/dL) possibly due to Gilbert's Syndrome should have a direct bilirubin checked. If the direct bilirubin is normal and medical history is suggestive/positive for Gilbert's Syndrome, the patient successfully meets the criteria.
9. Men and women of childbearing potential must use highly effective methods of contraception during the course of the treatment period and for at least 12 months after the last infusion of study drug. A man or woman is of childbearing potential if, in the opinion of the investigator, he or she is biologically capable of having children and is sexually active. Examples of highly effective contraception include:
 - combined (estrogen and progestogen containing) hormonal contraception associated with inhibition of ovulation ¹:
 - oral
 - intravaginal
 - transdermal
 - progestogen-only hormonal contraception associated with inhibition of ovulation 1:
 - oral
 - injectable
 - implantable ²
 - intrauterine device (IUD) ²
 - intrauterine hormone-releasing system (IUS) ²
 - bilateral tubal occlusion ²
 - vasectomised partner ^{2,3}

- sexual abstinence⁴

¹ Hormonal contraception may be susceptible to interaction with the study drug, which may reduce the efficacy of the contraception method.

² Contraception methods that in the context of this guidance are considered to have low user dependency.

³ Vasectomised partner is a highly effective birth control method provided that partner is the sole sexual partner of the study participant and that the vasectomised partner has received medical assessment of the surgical success.

⁴ In the context of this guidance sexual abstinence is considered a highly effective method only if defined as refraining from heterosexual intercourse during the entire period of risk associated with the study treatments. The reliability of sexual abstinence needs to be evaluated in relation to the duration of the clinical trial and the preferred and usual lifestyle of the subject.

10. Female patients of childbearing potential must have a negative serum pregnancy test at screening (Visit 1) and a negative urine pregnancy test on Day 1 (randomization, Visit 2). Females will be considered to be of non-childbearing potential if they fulfill one of the following criteria at screening:

- Postmenopausal defined as amenorrheic for at least 12 months following cessation of all exogenous treatments
- Documentation of irreversible surgical sterilization by hysterectomy, bilateral oophorectomy, or bilateral salpingectomy, but not tubal ligation.

11. Able to provide written informed consent, which must be obtained prior to any study-related procedures.

3.2.2 Exclusion Criteria

Patients will not be entered in the study for any of the following reasons:

1. Previous treatment with any chemotherapy and/or rituximab or other monoclonal antibody.
2. Prior radiotherapy completed <28 days before study enrollment.
3. Anticipated need for concomitant administration of any other experimental drug, or a concomitant chemotherapy, anticancer hormonal therapy, radiotherapy, or immunotherapy during study participation.
4. Concomitant disease which requires continuous therapy with corticosteroids at doses equivalent to prednisolone >20 mg/day.
5. Leukemia or transformation to diffuse large B cell lymphoma secondary to previously untreated follicular lymphoma.

6. Prior or concomitant malignancies within 5 years prior to screening, with the exceptions of non-melanoma skin cancer, adequately treated carcinoma in situ of the cervix, adequately treated breast cancer in situ, and localized prostate cancer stage T1c, provided that the patient underwent curative treatment and remains relapse free.
7. Patients with a body surface area $>3.0 \text{ m}^2$.
8. Major surgery (excluding lymph node biopsy) within 28 days prior to randomization.
9. Primary or secondary immunodeficiency (history of, or currently active), including known history of human immunodeficiency virus (HIV) infection or positive test at screening.
10. Acute, severe infection (e.g., sepsis and opportunistic infections), or active, chronic or persistent infection that might worsen with immunosuppressive treatment (e.g., herpes zoster).
11. Positive serological test for hepatitis B surface antigen (HBsAg), hepatitis B core antibody (HBcAb) or hepatitis C serology.
 - Patients with a negative HBsAg and positive HBcAb must have a hepatitis B virus (HBV) deoxyribonucleic acid (DNA) level $<20 \text{ IU/mL}$ (or 112 copies/mL) by polymerase chain reaction (PCR). These HBV patients must be willing to undergo PCR HBV DNA testing during study and may participate following consultation with a hepatitis expert regarding monitoring and use of HBV antiviral therapy, and provided that they agree to receive treatment as indicated. An HBV re-test will be performed at each study visit from Week 5 onwards, and at the discretion of the Investigator.
 - Patients with a positive test because of HBV vaccine may be included (i.e., anti-HBs+, anti-HBc-).
 - Patients positive for hepatitis C virus (HCV) antibody are eligible only if PCR is negative for HCV ribonucleic acid (RNA).
12. Confirmed current active tuberculosis (TB).
 - Patients with latent TB as determined by tuberculosis skin testing (e.g. Mantoux test) or interferon-gamma release assay (IGRA e.g. QuantiFERON-TB test) may be enrolled if such patients have written confirmation from their health care provider (e.g., Pulmonologist or Infection Specialist) of adequate prophylaxis before or within the screening period, and no evidence of tuberculosis on a chest X-ray performed within 3 months of Day 1 or chest CT.
 - TB testing is required only if it is required by local regulation or at the investigator's discretion.

13. Central nervous system (CNS) or meningeal involvement, or cord compression by the lymphoma; history of CNS lymphoma. A brain scan (CT or MRI) should be conducted at screening ONLY if lesions are suspected on the brain, to exclude patients with brain localization of FL.
14. History of a severe allergic reaction or anaphylactic reaction to a biological agent or history of hypersensitivity to any component of the trial drug (e.g., hypersensitivity or allergy to murine products).
15. Patients who have significant cardiac disease, including but not limited to history of congestive heart failure (New York Heart Association Class III/IV; see Appendix 7), unstable angina, or uncontrolled cardiac arrhythmia.
16. Uncontrolled or severe hypertension, or cerebrovascular disease.
17. Serious underlying medical conditions that, per the Investigator's discretion, could impair the ability of the patient to participate in the trial (including but not limited to ongoing active infection, severe immunosuppression, uncontrolled diabetes mellitus, gastric ulcers, or active autoimmune disease).
18. Any other co-existing medical or psychological condition(s) that will preclude participation in the study or compromise ability to give informed consent and/or comply with study procedures.
19. Treatment with any investigational medicinal product (IMP) within 4 weeks prior to initiation of 1st infusion of study drug, or treatment with a drug that has not received regulatory approval for any indication within 4 weeks or a minimum of 5 half-lives, whichever is longer, of the 1st infusion of study drug.
20. Receipt of a live/attenuated vaccine within 6 weeks prior to the screening visit.
21. Females who are pregnant, breastfeeding, or planning a pregnancy during the treatment period or within 12 months after the last infusion of study drug.
22. Patients who are investigational site staff members directly involved in the conduct of the trial, and their family members, site staff members otherwise supervised by the investigator, or patients who are Archigen employees directly involved in the conduct of the trial.

3.2.3 Patient Restrictions

For details of medications prohibited before and during the study, please refer to the inclusion and exclusion criteria (Sections 3.2.1 and 3.2.2) and to Section 4.11.

Since hypotension may occur during rituximab infusion, consideration should be given to withholding anti-hypertensive medications 12 hours prior to the infusion.

There are no other study restrictions.

3.3 Stopping Rules, Withdrawal Criteria, and Procedures

3.3.1 Patient Withdrawal

All patients are free to withdraw from participation in the study at any time, for any reason, specified or unspecified, and without prejudice to further treatment. The criteria for enrollment are to be followed explicitly.

In addition, patients may be withdrawn from study drug and/or from the study in the circumstances outlined below.

Distinction should be made between discontinuation of study drug treatment and withdrawal from the study, and the reason for treatment discontinuation or study withdrawal should be recorded by the Investigator. The Sponsor should be notified promptly when a patient is withdrawn from either study drug treatment or the study.

3.3.1.1 Withdrawal from Study

Patients may be withdrawn from the study for the following reasons:

- a) The patient is unwilling to continue in the study (i.e., withdraws consent). In this case, no more investigations will be performed. The patient does not have to justify their decision.
- b) The patient is lost to follow-up despite reasonable efforts to make contact with the patient. In this case, all attempts to contact the patient, request to return for visit and information received during contact attempts must be documented in the patient's medical record. In any circumstances, every effort should be made to document patient outcome, the reason for withdrawal, and any unresolved or new AEs.
- c) The Sponsor stops the study (see Section 3.3.2) or closes an individual study site (see Section 3.3.3) due to critical non-compliance with study protocol, ICH-GCP or other applicable regulatory requirements.

Patients who are withdrawn from the study will not be replaced.

Adverse events will be followed up as detailed in Section 6.10. Investigators are encouraged to discuss the patient's case with the Sponsor physician or representative to agree upon appropriate action. For patients who need to be withdrawn from the study early, it is highly

recommended that efficacy assessments are conducted at Week 28. Once a patient is withdrawn from the study, no further assessments can be conducted.

3.3.1.2 Discontinuation of Study Drug

An individual patient may be discontinued from study drug treatment for the following reasons:

- Prohibited treatment such as any other experimental drug or a concomitant chemotherapy, anticancer hormonal therapy, radiotherapy, or immunotherapy.
- Lack of compliance with protocol (e.g., refusal or inability to adhere to the study schedule or procedures).
- Patients who meet any of the following specific safety discontinuation criteria:
 - Patients who develop severe (common terminology criteria for adverse events [CTCAE] Grade 3 or above) infusion-related reactions, especially severe dyspnea, bronchospasm, or hypoxia, should have the infusion interrupted immediately to receive aggressive symptomatic treatment. In all patients, the infusion should not be restarted on the same day until complete resolution of all symptoms. At this time, the infusion may be initially resumed at the discretion of the Investigator at not more than one-half the previous rate. If the reaction was an anaphylactic reaction, or if the same infusion-related reaction occurs for a second time, the infusion should be permanently discontinued (refer to Section 4.5).
 - Active TB.
 - Invasive fungal infection or opportunistic infection including, but not limited to, listeriosis, legionellosis, or pneumocystis.
 - Hepatitis B virus reactivation or hepatic failure.
 - PML: neurological warning signs include major changes in vision, unusual eye movements, loss of balance or coordination, and disorientation or confusion.
 - Cancer: any new malignant lesion. Patients with basal cell and squamous cell carcinomas of the skin or carcinoma in situ of the cervix uteri that has been excised and cured, may be continued on the study at the discretion of the Investigator. If such carcinomas develop during the study, they may be excised and the patient may continue on the study.
 - Any other AEs which, in the opinion of the Investigator or the Sponsor, could compromise the patient's safety or well-being if they continued to participate in the study.

- Pregnancy in a female participant.

Assessments for patients who discontinue the study drug early

Patients who discontinue the study drug early for any reason will be required to have efficacy assessments at Week 28, and an early treatment discontinuation visit. If new treatment must be started before the Week 28 assessments, then an early treatment discontinuation visit, including a CT scan (see Table 1), should be performed before the start of the new treatment. Patient who discontinue the study treatment will be followed-up until Week 52 (EOS) for safety and immunogenicity.

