6.4.6 Infusion Reactions

An acute onset infusion reaction generally occurs within 24 hours of infusion of the study drug. Rituximab can cause severe, including fatal, infusion reactions. Severe reactions typically occur during the first infusion with time to onset of 30 to 120 minutes. Rituximab-induced infusion reactions and sequelae include headache, nausea, fever or chills, dizziness, flush, urticaria, hypotension, angioedema, hypoxia, bronchospasm, pulmonary infiltrates, acute respiratory distress syndrome, myocardial infarction, chest or back pain, ventricular fibrillation, cardiogenic shock, anaphylactoid events, or death. Distinction between infusion reaction and anaphylaxis is necessary.

Medical management (e.g., glucocorticoids, epinephrine, bronchodilators, or oxygen) for infusion reactions must be instituted as needed. Depending on the severity of the infusion reaction and the required interventions, rituximab may be temporarily or permanently discontinued. If the same severe (Grade 3) or above infusion reaction occurs for a second time, the decision to discontinue permanently should be seriously considered. Resume infusion at a minimum 50% reduction in rate after symptoms have resolved (see Appendix 8). Closely monitor patients with pre-existing cardiac or pulmonary conditions.

.Please refer also to Section 6.4.3 (Anaphylactic Reactions) for differential diagnosis with anaphylaxis.

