6.8 Recording of Adverse Events

After the patient has signed the ICF, but prior to initiation of study drug, only SAEs caused by a protocol-mandated procedure should be reported (e.g., SAEs related to invasive procedures such as biopsies).

After initiation of study drug upto 60 days after last dose, all AEs/SAEs, regardless of relationship to study drug, will be reported until the EOS visit. After 60 days from last dose, AEs/SAEs assessed as 'related' will be reported until EOS visit. However, all AESIs should be reported regardless of relationship until EOS regardless of the time elapsed since last dose of study drug.

Adverse events continuing at the EOS visit must be followed until recovery, or if persistent, until sufficient characterization has been achieved or the Investigator and Sponsor (or representative) agree to not follow them further.

Each AE is to be evaluated for duration, severity, seriousness, and causal relationship to the investigational drug. The action taken with study drug and the outcome must also be recorded.

Severity

The investigator will grade severity as mild, moderate, severe, life-threatening, or death, according to the US NCI-CTCAE version 4.03. A printable version of the criteria can be found at:

http://evs.nci.nih.gov/ftp1/CTCAE/CTCAE_4.03_2010-06-14_QuickReference_8.5x11.pdf

Note the distinction between the severity and the seriousness of an AE. A severe event is not necessarily a SAE. For example, a pain may be severe (interferes significantly with patient's usual function), but would not be classified as serious unless it met one of the criteria for SAEs.

Relationship

The causal relationship of the study drug to all AEs occurring after the start of study drug infusion will be assessed as one of the following two categories.

1. **Unrelated** (AE for which relationship to the study drug can be ruled out). A reasonable possibility of the AE occurring is considered highly unlikely for one of the following reasons:
 - Occurrence of the event can be expected based on the patient's underlying disease, concurrent illness, or medical history.
 - Occurrence of the event can be expected based on the patient's age, gender, or other characteristics.
 - There is no apparent temporal relationship between study drug infusion and occurrence of the event. Example: Occurrence of an AE after a considerable length of time has elapsed since completion or discontinuation of study drug infusion.

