6. In patients with detectable circulating malignant cells, it is strongly advised that the initial infusion rate be reduced to 25 mg/hour; these patients may experience more frequent and severe transient fever and rigors, shortness of breath, and hypotension.
 7. The exact date and time of start of infusion, end of infusion, any interruptions (stop time, restart time etc.), and total dose administered must be recorded in the patient's eCRF.

Table 1 Recommended Infusion Rates

Day 1 infusion	Dose (mg)	Time (minutes) ^a	Cumulative dose (mg)	Day 8, 15, and 22 infusions	Dose (mg)	Time (minutes) ^a	Cumulative dose (mg)
50 mg/h	50	0-60	50	100 mg/h	50	0-30	50
100 mg/h	50	61-90	100	200 mg/h	100	31-60	150
150 mg/h	75	91-120	175	300 mg/h	150	61-90	300
200 mg/h	100	121-150	275	400 mg/h	(375*BSA)-300	^d	^d
250 mg/h	125	151-180	400				
300 mg/h	150	181-210	550				
350 mg/h	175	211-240 ^b	725				
400 mg/h	(375*BSA)-725	^c	^c				

BSA body surface area in m²

- a Allowed window for infusion rate time at each time point is \pm 5 minutes.
- b Approximately 240 minutes (4 hours) to complete a dose of 725 mg.
- c Total dose and time of infusion will depend on patient's BSA. Total dose is 375 mg/m²; every additional 50 mg above a 725 mg dose will require 7.5 minutes infusion of the 400 mg/mL dose.
- d Total dose and time of infusion will depend on patient's BSA. Total dose is 375 mg/m²; every additional 50 mg above a 300 mg dose will require 7.5 minutes infusion of the 400 mg/mL dose.

If the patient experiences fever and rigors, or any ADR, the antibody infusion should be discontinued, and the severity of the side effects evaluated. If the symptoms improve, the infusion may be continued, initially at one-half the previous rate. The Investigator should wait an additional 30 minutes while delivering the infusion at the reduced rate. If tolerated, the rate may then be increased to the next closest rate on the patient's infusion schedule. For example:

(Example 1) An infusion-related reaction or an ADR at a rate of 50 mg/h → change rate to 25 mg/h → reaction resolved → additional 30 minutes at a rate of 25 mg/h → change back to 50 mg/h

(Example 2) An infusion-related reaction or an ADR at a rate of 300 mg/h → change rate to 150 mg/h → reaction resolved → additional 30 minutes at a rate of 150 mg/h → change back to 200 mg/h.

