If the patient does not tolerate the reduced rate for at least 30 minutes then the infusion should be stopped and the patient discontinued from the study.

Drug infusions will take place under the close supervision of an experienced physician, and in an environment where full resuscitation facilities are immediately available. Although the study drug will be administered on an outpatient basis, and patients discharged after the infusion in accordance with the normal standard of care for rituximab-containing regimens, patients may be hospitalized for observation at the discretion of the Investigator, and such instances of planned hospitalization will NOT be recorded as a serious adverse event (SAE).

Any drugs that are used to manage hypersensitivity reactions or ADRs, including but not limited to epinephrine, antihistamine, and corticosteroid, should be immediately available in case of emergency.

Attention should be given to the development of anaphylaxis during infusion of the study drug. When an anaphylactic reaction is suspected during infusion of the study drug:

- Discontinue the study drug.
- Apply a tourniquet close to the infusion site in order to slow systemic absorption of the study drug. Do not block artery flow.
- Perform appropriate airway management.
- If required, administer antihistamine, epinephrine, or other drugs.
- Closely monitor the patient and document the observations.

Similarly, in the event of any other life-threatening reaction, including hypersensitivity reaction, renal failure, severe cardiopulmonary event and severe mucocutaneous reaction, the study drug will be discontinued and no additional study drug will be administered.

If extravasation occurs during infusion of the study drug, the infusion must be stopped. Restart the remainder of the infusion either in the area of the same arm that is proximal to the body, or in the other arm. The PK, PD and immunogenicity samples will always be drawn from the opposite arm of the infusion arm.

Following the infusion, the i.v. line should be maintained for medications as needed. If there are no complications after 1 hour of observation, the i.v. line may be discontinued. The i.v. line may not be used for sampling for PK, PD, or immunogenicity.

Institutional guidelines for the administration of rituximab, and the kind of premedication, can be followed. Dose modification is not permitted during this study. Any deviation to the dose will be recorded in the eCRF.

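### Section 3.3.1.2 allows a half-rate restart after a first, resolved, non-anaphylactic life-threatening infusion reaction, which Appendix 8 forbids

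*Protocol*

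**What the plan says.** Protocol Section 3.3.1.2 lists the safety criteria for stopping study drug. Its first item covers CTCAE "Grade 3 or above) infusion-related reactions, especially severe dyspnea, bronchospasm, or hypoxia". The infusion is interrupted and symptoms are treated. Once they have resolved completely, the text continues: "At this time, the infusion may be initially resumed at the discretion of the Investigator at not more than one-half the previous rate". Two exceptions follow: "If the reaction was an anaphylactic reaction, or if the same infusion-related reaction occurs for a second time, the infusion should be permanently discontinued". The only cross-reference at that point is to Section 4.5.

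Section 6.8 sets the severity scale: "The investigator will grade severity as mild, moderate, severe, life-threatening, or death, according to the US NCI-CTCAE version 4.03".

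Appendix 8 has a restart rule of its own: "If the symptoms improve, the infusion may be continued, initially at one-half the previous rate". After its instructions on anaphylaxis, it limits that rule. The trigger for the limit is worded "in the event of any other life-threatening reaction, including hypersensitivity reaction, renal failure, severe cardiopulmonary event and severe mucocutaneous reaction". The action it then requires leaves no choice to the site: "the study drug will be discontinued and no additional study drug will be administered".

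Sections 4.5 and 6.4.6 say that stopping may be temporary or permanent depending on severity, and that the infusion resumes at a rate cut by at least half once symptoms resolve. Neither section states the exception for life-threatening reactions.

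**The concern.** The scale in Section 6.8 places life-threatening directly above severe, so a rule for Grade 3 and higher takes in Grade 4. For a first Grade 4 infusion reaction that is not anaphylaxis and has resolved, Section 3.3.1.2 leaves a restart to the Investigator, while Appendix 8 leaves no discretion.

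The stake is patient safety. Sections 1.3 and 6.4.6 both say that rituximab infusion reactions can be fatal, yet the section a site would consult on stopping drug gives written permission to re-expose the patient. Sites could also handle the same event differently. With about 165 sites for about 308 patients (308 / 165 = 1.9 per site), consistent handling depends on the written rule.

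**Working it through.** There is no planned figure to reproduce. The check compares the texts and then sizes the exposure at issue.

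**1. The rules side by side, for a first, fully resolved infusion reaction**

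| Reaction | Section 3.3.1.2 | Appendix 8 | Conflict? |
|---|---|---|---|
| Grade 3, not anaphylaxis | Restart at half rate or less, at the Investigator's discretion | Half-rate restart if symptoms improve | Not on this point |
| Anaphylaxis | Permanent stop | Stop | No |
| Grade 4, not anaphylaxis | Restart at half rate or less, at the Investigator's discretion | Stop, no further study drug | **Yes** |

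**2. Do the two texts cover the same events?** They do. Section 1.3 gives hypersensitivity reactions as an example of severe infusion reactions, and Appendix 8 names hypersensitivity under its stop rule. Section 6.4.6 counts bronchospasm, acute respiratory distress syndrome, myocardial infarction, ventricular fibrillation and cardiogenic shock among infusion reactions and their sequelae. Appendix 8 names severe cardiopulmonary events.

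**3. Do the cross-references settle it?** They do not. Section 3.3.1.2 points to 4.5. The pointer in 4.5 at the resume step is to the rate table in Appendix 8, and 6.4.6 cites Appendix 8 for resuming. None of these sections repeats the stop rule, and no statement was found of which text prevails.

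**4. How much drug is at issue per patient?**

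Inputs:
- Timing (Section 6.4.6): "Severe reactions typically occur during the first infusion with time to onset of 30 to 120 minutes".
- Day 1 rates (Appendix 8, Table 1): 50 mg/h for the first 60 minutes, 100 mg/h for the next 30, then 150 mg/h for the next 30.
- Course: 4 × 375 mg/m².
- Body surface area: 1.5 to 2.2 m², an assumption.

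Given by 30 minutes: 50 × 0.5 = 25 mg.
Given by 120 minutes: 50 × 1 + 100 × 0.5 + 150 × 0.5 = 175 mg.
Remaining course = 4 × 375 × BSA − amount given.

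| BSA (m²) | Full course (mg) | Remaining at 30 min | Remaining at 120 min |
|---|---|---|---|
| 1.5 | 2,250 | 2,225 mg (98.9%) | 2,075 mg (92.2%) |
| 1.8 | 2,700 | 2,675 mg (99.1%) | 2,525 mg (93.5%) |
| 2.2 | 3,300 | 3,275 mg (99.2%) | 3,125 mg (94.7%) |

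For the interrupted first infusion alone, the remainder is 375 × BSA − amount given. The smallest value is 375 × 1.5 − 175 = 387.5 mg (387.5 / 2,250 = 17% of the course). The largest is 375 × 2.2 − 25 = 800 mg (800 / 3,300 = 24%).

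**5. How many patients?** The documents give no rate. At an assumed 0.5% to 2%: 308 × 0.005 = 1.5 and 308 × 0.02 = 6.2, so about 2 to 6 patients.

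**The case against.** The strongest reply is that the texts can be read together. Section 3.3.1.2 only permits, Appendix 8 commands, and a site that stops satisfies both. On that reading the specific stop limits the general permission, just as it limits Appendix 8's own restart rule. Section 4.8 also names Appendix 8 as the source of infusion instructions. The safety list in 3.3.1.2 ends with a catch-all for any adverse event judged to endanger the patient, and Sections 4.5 and 6.4.6 let severity justify a permanent stop. A careful Investigator would probably stop.

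This shows that stopping is always allowed. It does not make stopping required: the catch-all and the severity wording are matters of judgment, whereas Appendix 8 imposes a duty. An Investigator can follow 3.3.1.2 to the letter and still breach Appendix 8.

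Three narrower points stand in part:
- Table 3 in Section 6.4.3 defines anaphylaxis broadly, so many life-threatening reactions already fall under a mandatory stop. The remaining gap is small, though single-system events keep it from being empty.
- The restart sentence concerns the interrupted infusion, which is 17% to 24% of the course. The 92% to 99% figure counts everything Appendix 8 would withhold; the later doses follow because 3.3.1.2 does not discontinue the patient.
- Section 4.5 defers to local product labeling where it differs. That labeling is not in the documents, so actual site practice cannot be predicted.

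**Conclusion.** The concern holds and should be fixed. Its scope is a first, fully resolved, non-anaphylactic, life-threatening infusion reaction. Grade 3 reactions that are not life-threatening are handled consistently on this point.

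For an affected patient, the texts differ over 92% to 99% of the planned course, given the assumed body surface areas and the onset window in Section 6.4.6. The figure of about 2 to 6 patients rests wholly on the assumed rate and is not evidence of frequency.

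The effect on the primary analysis is small. Treatment is blinded and randomized 1:1, the primary set is the FAS, and patients who stop drug early are still to have Week 28 efficacy assessments. The reason to act is safety.

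**What to change.** - **Section 3.3.1.2:** limit the restart sentence to Grade 3, non-anaphylactic reactions. Add that after any life-threatening (Grade 4) infusion reaction study drug is permanently discontinued and no further dose is given, with a reference to Appendix 8.
- **Sections 4.5 and 6.4.6:** add to each resume sentence an exception for life-threatening (Grade 4) reactions.
- **Appendix 8:** leave the stop rule as it is.
- **Sites:** send a short notice of the change.

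The cost is a few clauses and the notice, with no added patients or data. The downside is that an occasional patient loses remaining doses that an Investigator might have chosen to give, which the sponsor's own Appendix 8 rule already entails.
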